7.7 STUDY COMPLETION PROCEDURES

A study Exit Form must be completed for all subjects enrolled in the study upon subject completion, withdrawal or discontinuation.

7.7.1 SUBJECT COMPLETION

Subjects are considered to have completed the study if they have completed the Postop Month 6 or later visit.

Subjects with ocular serious adverse events or adverse device effects that are unresolved at study exit should continue to be followed until resolution of the event or until they are stable per the investigator's evaluation.

7.7.2 SUBJECT WITHDRAWAL PRIOR TO IMPLANTATION

Subjects may be withdrawn from the study prior to implantation if they do not meet all inclusion/exclusion criteria (screen failures) or decide not to participate in the study.

7.7.3 SUBJECT WITHDRAWAL DUE TO INTRAOPERATIVE COMPLICATIONS PRIOR TO IMPLANTATION

Subjects that meet all inclusion/exclusion criteria but do not undergo implantation of a LAL IOL due to intraoperative complications prior to introduction of the LAL will be followed to resolution of any adverse events and then exited from the study.

7.7.4 SUBJECT DISCONTINUATION AFTER IMPLANTATION

After LAL implantation, subjects may not be withdrawn from the study unless the LAL or LALs (in the case of bilaterally implanted subjects) have been explanted. In the case of an explant, the investigator should continue follow-up for a period that ensures no adverse consequences have resulted. When possible, all necessary clinical assessments will be performed prior to the Subject exiting the study even if the assessment was not scheduled at that particular visit.

Subjects may be discontinued from the study only if the LAL or LALs (in the case of bilaterally implanted subjects) have been explanted or subject has deceased. The reason for discontinuation will be recorded on the appropriate study worksheet. Subjects who are discontinued from the study will still be a part of the study analyses up until the point they are exited.

7.7.5 LOST TO FOLLOW-UP

Subjects for which the final post-operative case report form is overdue and who refuse to be followed, or have difficulty being followed, or cannot be contacted despite extensive written and telephone follow-ups to determine the final clinical outcome, will be considered lost to follow-up. Sites must make a minimum of three documented attempts via telephone, email, or regular mail to contact the subject. If the subject does not reply to any of these attempts, the site must send a letter by certified mail (with a request for notification of receipt of delivery) to the subject. If a subject is non-responsive to these follow-up attempts, the subject will be considered to be lost to follow-up.

7.7.6 STUDY TERMINATION

The study may be stopped at any time by the Sponsor(s) for reasonable cause with appropriate notification. Conditions that may warrant study termination include, but are not limited to the following:

- Safety concerns. Clinical data from the study will be monitored to assure the safety of enrolled subjects.

If the clinical study is prematurely terminated, the Sponsor will inform the Investigator, Ethics Committee, and other appropriate regulatory bodies. If the Sponsor terminates the study for safety reasons, it will immediately notify the Investigator, Ethics Committee, and other appropriate regulatory bodies and provide an explanation of the reasons for termination. The Investigator will be provided with instructions for study termination and

applicable subject follow-up. The Sponsor will continue to provide resources to fulfill the Clinical Study Plan obligations for follow-up of the subjects enrolled in the study.

8 STATISTICAL METHODS

8.1 POPULATIONS FOR ANALYSIS

Exploratory effectiveness analyses will be performed on all eyes as specified. Clinical data for former CSP-037-MX study eyes may be analyzed separately.

Safety analyses will be performed on observed data for all eyes of subjects who sign the informed consent and the procedure was attempted which is defined as the point at which the LAL makes contact with the eye. No imputation will be performed.

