7.4 EXAMINATION SCHEDULE

Evaluation	Subjects who did not previously participate in CSP-037-MX or Former CSP-037-MX subjects with fellow eye (CSP-037-MX non-study eye) enrolled	Former CSP-037-MX subjects with only former CSP-037-MX study eye enrolled
Preoperative	Day -60 to Day -1	NA
Operative	Day 0, day of surgery	NA
Postop Day 1	Days 1 to 2 postop	NA
¹	Days 7-14 postop	NA
Postop Week 3	Days 17 to 30 days postop: Adjustment #1	Days 17 to 30 days postop: Adjustment #1
Adjustment #2, if needed	2 to 7 days post Adjustment #1	2 to 7 days post Adjustment #1
Adjustment #3, if needed	2 to 7 days post Adjustment #2	2 to 7 days post Adjustment #2
Lock-in #1	2 to 7 days post final adjustment	2 to 7 days post final adjustment
Lock-in #2, if needed	2 to 7 days post lock-in #1	2 to 7 days post lock-in #1
Post Lock-in	7 to 14 days post final lock-in	7 to 14 days post final lock-in
Postop Month 3	Days 90 to 150 postop	Days 90 to 150 postop
Postop Month 6 or later	Days 180 to 400 postop	Days 180 to 400 postop

¹ Subgroup of eyes determined by the principal investigator

Unscheduled visits falling outside the designated ranges for scheduled visits will be considered “interim” visits for data recording purposes. A report form will be completed for interim visits on the study eye.

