Visits	Preop*	Operative*	Postop Day 1*	[REDACTED] *	Postop Week 3	Adjustment #2 (if needed)	Adjustment #3 (if needed)	Lock-in #1	Lock-in #2 (if needed)	Post Lock-in	Postop Month 3	Postop Month 6 or later	Unscheduled Visit ³
Slit Lamp Exam	X		X	X	X	X	X	X	X	X	X	X	
Fundus Exam	X				X						X	X	
Aberrometry	X			X	X	X	X	X	X	X	X	X	
Dilated Pupil Diameter	X				X	X	X	X	X				
Adverse Events		X	X	X	X	X	X	X	X	X	X	X	X

¹ Only performed on subjects with both eyes enrolled and successfully implanted

^{1.1} Only performed on subjects with both eyes enrolled and successfully implanted and subject did not have an [REDACTED] visit

² May be performed on a subgroup of subjects as described in section 7.3.2.2 of the protocol

³ Tests indicated with an "X" must be performed at each unscheduled visit. Other tests may be conducted based on the investigator's assessment of the subject.

⁴ Only required for subjects who previously participated in RxSight's CSP-037-MX study

⁵ Only performed on subjects who did not have an [REDACTED] visit

*Visits only required for subjects who did not previously participate in RxSight's CSP-037-MX study

** Subgroup of eyes based on decision made by Principal Investigator

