8.2.2 ADDITIONAL SAFETY ANALYSES

The safety outcomes will be summarized descriptively for all eyes that have the procedure attempted.

BCDVA

Monocular BCDVA will be presented with the number and percent of eyes who fall into each category of BCDVA at each visit (e.g. 20/20 or better, 20/25 or better, 20/32 or better, etc.). The mean BCVDA logMAR score will be calculated for each visit. Change in BCVDA from Postop Week 3 or from Preoperative will be presented at each visit as categorical outcomes of “Increase in 15 letters or more”, “Increase in 10-14 letters”, “Increase in 5-9 letters”, “No change”, “Decrease in 5-9 letters”, “Decrease in 10-14 letters”, and “Decrease in 15 letters or more”.

In-Office Erythropisa Assessment

The number and percent of eyes in each outcome of erythropsia assessment (0- white, 1- pink, or 2- red) will be presented.

Intraocular Pressure (IOP)

The IOP and change in IOP from preoperative will be summarized by mean, standard deviation, median, minimum and maximum. The number and percent of eyes reported with $IOP \geq 25 \text{ mmHg}$ or an IOP increase of $\geq 10 \text{ mmHg}$ from preop will be provided at each visit.

Slit Lamp Examination and Fundus Examination Findings

The outcomes will be summarized descriptively by count and percent of eyes with each possible finding category.

⁸ McAlinden C, Pesudovs K, Moore JE. The Development of an Instrument to Measure Quality of Vision: The Quality of Vision (QoV) Questionnaire. *Invest Ophthalmol Vis Sci*. 2010;51:5537-5545.

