10.4.1 IDENTIFICATION AND COLLECTION

All AEs that occur during the study must be recorded in English on the adverse event Case Report Form. Each event must be on a separate form, regardless of whether one event may be secondary to another or from a single cause. Identification and collection of an AE begins after informed consent has been obtained and documented. Standard sources of identifying AEs include:

- direct observation by the Investigator or study team member
- asking the study participant a specific question (e.g., "Since your last visit, have you experienced any problems with your eyes or vision?")
- unsolicited volunteering of information by the study participant (e.g., "Doctor, I have had numerous headaches since I started using this lens.")

Ocular AEs and SAEs and systemic SAEs observed or elicited by the Investigator, reported by the subject, or resulting from a test result, etc., occurring during the clinical investigation must be documented. AE Forms are to be completed at the time of the event regardless of all data being available.

During the study, the Investigator should treat the study subject as appropriate to ensure his/her safety and welfare. Refer to Section 7.7.1 for additional information pertaining to ongoing AEs at subject exit.

Pre-existing conditions will not be considered AE/SAEs but will be collected at the Preoperative Visit as medical history. A worsening of a pre-existing condition during the study should be documented as an AE and evaluated accordingly.

Hospitalization is a criterion for assessment of seriousness. Hospitalization in the absence of a medical AE is not in itself an AE. For example, the following reports of hospitalization without a medical AE should not be considered either an SAE or an AE:

- Planned hospitalization for a pre-existing condition without serious deterioration in health (e.g., planned knee replacement surgery)
- Social admission (e.g., subject has no place to sleep)
- Administrative admission (e.g., for yearly physical exam or elective procedures not related to the study)
- Optional admission not associated with a precipitation medical AE (e.g., for elective cosmetic surgery)

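### If former CSP-037-MX eyes are enrolled and pooled, Section 8.1 counts them in the safety denominator, but their adverse events are collected only from CSP-036-MX consent, so a surgery-onward cumulative rate can only be biased downward

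*Combined protocol and SAP*

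**What the plan says.** **Who is in the safety set.** Section 8.1: "Safety analyses will be performed on observed data for all eyes of subjects who sign the informed consent and the procedure was attempted". The attempt is defined as "the point at which the LAL makes contact with the eye", with no limit on date or on the protocol under which it happened. Section 8.2.2 repeats the rule: "The safety outcomes will be summarized descriptively for all eyes that have the procedure attempted". Section 4 extends the safety evaluation to every study eye. Section 8.2 names cumulative events, by reference to ISO 11979-7, as part of the safety parameter.

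**Who the former eyes are.** Section 6 allows, but does not require, enrolment of subjects who already carry the lens from CSP-037-MX and have had no light treatment. Section 6.1 requires them to sign a new CSP-036-MX consent.

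**When their events are collected.** Section 10.4.1: "Identification and collection of an AE begins after informed consent has been obtained and documented". It adds: "Pre-existing conditions will not be considered AE/SAEs but will be collected at the Preoperative Visit as medical history", although a later worsening is an adverse event. Section 7.4 has a column headed "Former CSP-037-MX subjects with only former CSP-037-MX study eye enrolled", in which the preoperative, operative and Day 1 visits, and the visit at Days 7-14, are marked not applicable. The first visit is Week 3, Day 17 to 30 postop. The starred footnote to Table 1 (Section 7.5) agrees: "Visits only required for subjects who did not previously participate in" CSP-037-MX. Table 1, footnote 4, requires ocular history at Week 3 for former CSP-037-MX subjects only.

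**Separate analysis.** Section 8.1: "Clinical data for former CSP-037-MX study eyes may be analyzed separately". This is permission, not a commitment, and the available text of Sections 8.2 and 8.2.2 does not repeat it.

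**The concern.** An incidence is interpretable when numerator and denominator cover the same period at risk. Here they may not. In an eye operated on under CSP-036-MX, consent precedes surgery, so an early postoperative event is an adverse event even if it arises between visits and is reported at the next one. In a former eye, the same event before the new consent is history. That eye still adds one to the denominator.

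The study has no safety hypothesis, so no error rate is at stake. Descriptive incidence is, however, the only safety result it will produce, and Section 12.9 foresees publication. A team that follows the plan exactly could report one pooled cumulative rate in which some eyes were not observed for adverse events in the weeks just after surgery, without the table showing it.

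**Working it through.** The plan states no expected event rate, no number of former eyes and no sample-size derivation, so there is no figure of its own to reproduce. The check has three steps.

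**1. Same early event, two kinds of eye**

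| | Operated on under CSP-036-MX | Former CSP-037-MX eye |
|---|---|---|
| In the safety denominator (8.1, read literally) | Yes | Yes |
| Consent relative to surgery | Before | After; at the latest Day 17-30 |
| Operative and Day 1 visits (7.4, Table 1) | Yes | None in this study |
| Days 7-14 visit | Only if selected by the investigator | None in this study |
| Event after surgery, before the new consent | Adverse event | Ocular history at most |
| Event after light treatment | Adverse event | Adverse event |

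Only the numerator loses events, so the error cannot be upward.

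**2. Size**

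- *p*: true cumulative risk per eye from surgery. Assumed 3.0%, the same in both kinds of eye.
- *N*: 200 eyes, the maximum in Section 6.
- *f*: share of former eyes. Not given; may be 0. The documents describe one former study eye per subject, so at 200 eyes in 100 subjects the extreme is 100/200 = 50%.
- *e*: share of former eyes' events with onset before consent. Not given; 25% to 75% shown.

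Reported rate = *p* × (1 − *f* × *e*). Relative understatement = *f* × *e*, whatever *p* is. Expected eyes missed = *N* × *p* × *f* × *e* = 6 × *f* × *e*.

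| *f* | *e* = 25% | *e* = 50% | *e* = 75% | Eyes missed at *e* = 50% |
|---|---|---|---|---|
| 0% | 3.00% | 3.00% | 3.00% | 0 |
| 10% | 2.93% | 2.85% | 2.78% | 0.3 |
| 25% | 2.81% | 2.63% | 2.44% | 0.75 |
| 50% | 2.63% | 2.25% | 1.88% | 1.5 |

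For example, at *f* = 25% and *e* = 50%: 3.0% × (1 − 0.125) = 2.625%, or 5.25 eyes instead of 6.

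**3. Does restricting the denominator repair it?**

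Take *e* = 50%. For eyes operated on under CSP-036-MX only, the surgery-onward rate is 5.4/180 = 4.5/150 = 3.0/100 = 3.00% at *f* = 10%, 25% and 50%. Suppose the later half of events begins after first light treatment and every eye is treated. The pooled rate from first light treatment is then 3.0/200 = 1.50% at every *f*. Neither rate depends on the mix of eyes any longer.

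**The case against.** **The time origin is not in the documents.** They cite ISO 11979-7 for cumulative events and do not say where the count starts. If it covers only what is observed within this study, nothing is missing. This stands, and the conclusion is conditional on a surgery-onward reading.

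**Early events are not simply lost.** Footnote 4 of Table 1 takes ocular history at Week 3 in exactly these subjects, so an earlier complication can be on record. This also stands, but history does not enter the adverse-event numerator.

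**The sponsor may link the two studies.** Both have the same sponsor, and IOP change from preoperative (Section 8.2.2) would need earlier data for a former eye. Linkage may well be intended. The available text does not say so, and its Section 8.2 may be incomplete, so silence is weak evidence either way.

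**An attempt may mean one under this protocol.** Former eyes would then leave the safety set and take their light-treatment events with them, contrary to Section 4. The same sentence of Section 8.1 needs clarifying under either reading.

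**The sizes are assumed.** They are. Former eyes must also reach entry with the lens in place and adequate dilation. Those with serious early events may be less likely to enroll, so *f* × *e* may overstate what is missed.

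A reader might infer that the published rate will be understated, or that harm from light treatment will be undercounted. The documents support neither. Former eyes may not enrol or may have had no earlier event, and none had been light-treated before entry.

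**Conclusion.** The mismatch is in the text, but its effect is conditional. It needs former CSP-037-MX eyes to enrol, to have had events before the new consent, and to be pooled with the others without importing earlier records. It also assumes that cumulative incidence runs from surgery. When these hold, the pooled rate is too low by the relative amount *f* × *e*. In the illustration that is 0.15 percentage points at *f* = 10% and *e* = 50%, and 0.75 points at *f* = 50%. It is zero if no former eye enrols.

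Two things limit the consequence. All light-treatment exposure in former eyes falls within this study. A lasting finding would still appear in the Month 6 BCDVA, slit-lamp or fundus summaries, even if it is not listed as an adverse event. For a descriptive, exploratory study this is a minor point, worth correcting because the correction is cheap.

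**What to change.** In Sections 8.1 and 8.2:

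- Change *may* to *will* for a separate safety table of former CSP-037-MX eyes, reporting events with onset from CSP-036-MX consent.
- Report cumulative incidence from surgery only for eyes operated on under CSP-036-MX.
- Pool all eyes only for events with onset from first light treatment, over eyes with at least one such treatment.

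Alternatively, import the CSP-037-MX adverse events for these eyes from Day 0 and keep one pooled rate. That does not undo selection: an eye explanted before entry never becomes a former eye here.

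The first option costs a few lines of text and extra table rows; visits, treatment and sample size do not change. Its downside is a smaller denominator for surgical-period events: 180, 150 or 100 eyes instead of 200 if 10%, 25% or 50% are former eyes. The alternative keeps the full denominator but needs a data transfer between studies.

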8.1.1 EXPLORATORY EFFECTIVENESS PARAMETERS

Primary Exploratory Parameters

Eyes that received only non-presbyopic adjustments.

- % of eyes with UCDVA of 20/20 or better at Postop Month 6 or later

Eyes that received a presbyopia adjustment.

- Proportion of eyes simultaneously with (1) Monocular UCDVA of 20/25 or better and (2) Monocular UCIVA of 20/32 or better and (3) Monocular UCNVA of 20/40 or better at Postop Month 6 or later.

Clinical data for former CSP-037-MX study eyes may be analyzed separately.

Additional Exploratory Parameters

UCDVA

Monocular and/or binocular UCDVA will be presented with the number and percent of eyes that fall into each category of visual acuity performance (e.g. 20/20 or better, 20/25 or better, 20/32 or better, etc.) at each visit tested. Number and percent for eyes that only received non-presbyopic adjustments and for eyes that received a presbyopia adjustment may be presented separately. In addition, clinical data for former CSP-037-MX study eyes may be analyzed separately.

UCIVA, UCNVA, DCIVA, and DCNVA

Monocular and/or binocular UCIVA, UCNVA, DCIVA, and DCNVA for eyes that received a presbyopia adjustment will be presented with the number and percent of eyes that fall into each category of visual acuity performance (e.g. 20/20 or better, 20/25 or better, 20/32 or better, etc.) at each visit tested. In addition, clinical data for former CSP-037-MX study eyes may be analyzed separately.

Depth of Focus

The mean acuity across all eyes that received a presbyopia adjustment will be calculated and plotted separately. The mean, standard deviation, and confidence intervals for each point on the curve will be reported. In addition, clinical data for former CSP-037-MX study eyes may be analyzed separately.

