4 STUDY DESIGN

A prospective, single center, exploratory study will be conducted. Subjects will be followed until completion of the Postop Month 6 or later follow-up visit.

Patients who require cataract extraction and intraocular lens implantation will be pre-screened for eligibility as part of pre-entry activity. If one or both eyes meet inclusion/exclusion criteria, delegated and trained study staff will explain the study purpose, procedures, risks/benefits and subject responsibilities to the potential participant. Written informed consent must be obtained prior to initiation of any clinical procedures that are performed solely for the purpose of determining eligibility for research. The patient is enrolled upon signing the informed consent. Both eyes of all subjects may be screened for eligibility at the same preoperative visit. If at any time during the preoperative visit, an eye does not meet inclusion or exclusion criteria, screening for that eye can be discontinued immediately. If only one eye is being screened, then the subject will be exited from the study. If both eyes of the subject are enrolled for study participation, each eye will be scheduled for surgery within a timeframe of the investigator's choice but on separate days.

Patients from RxSight's CSP-037-MX study may have both eyes screened for study eligibility. The former CSP-037-MX study eye must meet all inclusion/exclusion criteria as specified below for subjects who previously participated in CSP-037-MX. If applicable, the fellow eye (CSP-037-MX non-study eye) must meet all inclusion/exclusion criteria as specified below for subjects who did not previously participate in CSP-037-MX. If only the prior CSP-037-MX study eye is being considered for this study, the subject will need to review and sign only a CSP-036-MX written informed consent for former CSP-037-MX subjects. If both eyes are being considered for this study, the subject will also have to review and sign a CSP-036-MX written informed consent for subjects who had no affiliation with CSP-037-MX.

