6 STUDY POPULATION

The study population will consist of up to 200 eyes in up to 100 subjects implanted with the LAL. A subset of the population may include study subjects who were already implanted with the LAL under RxSight's CSP-037-MX protocol "A Single Center Exploratory Study to Evaluate the Effects of Ambient Sunlight Exposure on the RxSight Light Adjustable Lens (LAL)" but who have not received light treatments with the LDD. Subject's eyes must meet all applicable inclusion criteria and none of the exclusion criteria as described.

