6.1 INCLUSION CRITERIA FOR SUBJECTS WHO DID NOT PREVIOUSLY PARTICIPATE IN CSP-037-MX

- Must sign a written Informed Consent form and be willing to undergo cataract surgery for the implantation of the LAL.
- Ages 30 or older on the day the cataract surgery is performed.
- Preoperative keratometric cylinder ≤ 3.50 D.

- Study eye must have a cataract causing reduction in best corrected distance visual acuity (BCDVA) to a level of 20/32 or worse with or without a glare source.
- In subjects with only one eye enrolled in the study: Potential for BCDVA of 20/40 or better in the non-study eye after cataract removal and IOL implantation.
- Study eye has BCDVA projected to be 20/20 or better after cataract removal and IOL implantation as estimated by potential acuity meter (PAM) or surgeon estimation.
- Study eye has clear intraocular media other than cataract.
- Willing and able to comply with the requirements for study specific procedures and visits.
- Study eye has average dilated pupil diameter of ≥ 7.0 mm.
- Study eye requires an IOL power within the range available for the LAL.

INCLUSION CRITERIA FOR SUBJECTS WHO PREVIOUSLY PARTICIPATED IN CSP-037-MX

- Subject was previously enrolled within clinical study CSP-037-MX sponsored by RxSight, Inc. and meets the following inclusion criteria:
 - Must sign a CSP-036-MX written informed consent specific for former CSP-037-MX subjects
 - Potential for BCDVA of 20/40 or better in the non-study eye currently
 - Willing and able to comply with the requirements for study specific procedures and visits.
 - Former CSP-037-MX study eye can adequately dilate (enough of the edge of the LAL optic can be visualized to allow for centration during LDD light treatment).

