7.3.2.2 Additional Clinical Testing

Additional clinical testing may be performed on a subgroup of study subjects. The Principal Investigator may determine whether a subject will be included into a clinical test subgroup based on the adjustment light treatments to be performed. Clinical measurement subgroups will include:

- Undilated photopic pupil diameter (Week 3, Post Lock-In, Month 3, Month 6 or later)
- Binocular UCDVA, UCIVA, UCNVA (Week 3, Post Lock-In, Month 3, Month 6 or later)
- Depth of Focus (Week 3, Lock-In #1, Post Lock-In, Month 3, Month 6 or later)
- Monocular DCIVA, DCNVA, UCIVA, UCNVA (Week 3, Lock-In #1, Post Lock-In, Month 3, Month 6 or later)
- Monocular Distance Corrected Contrast Sensitivity (Photopic/Mesopic) (Week 3, Post Lock-In, Month 3, Month 6 or later)
- [REDACTED]
- Posterior Segment SD-OCT

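### Section 8.1.1 plans depth-of-focus confidence intervals across eyes with no level, method or allowance for fellow eyes, and counts binocular acuity in eyes although it is one value per subject (minor)

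*Combined protocol and SAP*

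**What the plan says.** **Depth of focus.** Section 8.1.1 states: "The mean acuity across all eyes that received a presbyopia adjustment will be calculated and plotted separately". It then commits to intervals: "The mean, standard deviation, and confidence intervals for each point on the curve will be reported". These are the only confidence intervals in the visible statistical text. No level, sidedness, formula or treatment of fellow eyes accompanies them. Section 8.1 also names the eye as the unit: "Exploratory effectiveness analyses will be performed on all eyes as specified".

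**Where pairs come from.** Section 6 sets the cap: "The study population will consist of up to 200 eyes in up to 100 subjects implanted with the LAL". Section 4 provides for bilateral enrolment ("If both eyes of the subject are enrolled for study participation, each eye will be scheduled for surgery") and Section 6.1 for one-eye enrolment ("In subjects with only one eye enrolled in the study"). Depth of focus is one of the optional tests in Section 7.3.2.2, where the Principal Investigator may "determine whether a subject will be included into a clinical test subgroup based on the adjustment light treatments to be performed". The choice is therefore made by subject, and both eyes of one person can enter the curve.

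**Binocular acuity.** Section 8.1.1 covers monocular and binocular acuity in shared sentences and expresses both as counts and percentages of eyes. Footnote 1 to Table 1, attached to the binocular UCDVA row, limits that test to subjects with both eyes enrolled and implanted.

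**Grouping.** Section 8.1.1 groups by eye. The synopsis (Study Design) and Section 4 group uncorrected acuity by subject: those who had only non-presbyopic adjustments, and those who had a presbyopia adjustment.

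**The concern.** Two eyes of one person usually carry less information than two eyes of two people. A standard error formed as the eye-level SD over the square root of the number of eyes ignores this. The published curve would then suggest more precision than the data hold, and a reader could not tell what the interval represents, because neither its level nor its method is stated.

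The binocular problem is one of units and needs no assumption about correlation. A binocular acuity is one measurement per subject. If it is tabulated in eyes, the denominator no longer equals the number of observations.

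**Working it through.** The plan gives no interval width, level or calculated sample size, so there is no figure of its own to reproduce. The 200 eyes and 100 subjects are caps.

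**(a) Depth-of-focus interval**

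Input from the documents: at most 200/100 = 2 eyes per subject.

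Assumptions, none of them given in the documents:
- monocular testing;
- a 95% level;
- an eye-level interval;
- fellow-eye correlation rho of 0.3 or 0.5;
- share b of tested subjects with both eyes in the curve.

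With G subjects there are N = G(1 + b) eyes and Gb pairs. The variance of the simple mean across eyes is (SD²/N) × [1 + rho × 2b/(1 + b)]. Writing s = 2b/(1 + b) for the share of eyes that are paired:

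- SE factor (correct over eye-level) = sqrt(1 + rho × s)
- coverage of the nominal 95% eye-level interval = 2Φ(1.96/factor) − 1

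| b | s | Factor, rho 0.3 | Factor, rho 0.5 | Coverage, rho 0.3 | Coverage, rho 0.5 |
|---|---|---|---|---|---|
| 0.10 | 0.18 | 1.027 | 1.044 | 94.4% | 93.9% |
| 0.25 | 0.40 | 1.058 | 1.095 | 93.6% | 92.6% |
| 0.50 | 0.67 | 1.095 | 1.155 | 92.6% | 91.0% |
| 1.00 | 1.00 | 1.140 | 1.225 | 91.4% | 89.0% |

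If b = 0 or rho = 0, the factor is 1 and there is no effect.

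At the cap (100 subjects, all paired), the eye-level half-width is 0.139 SD. The correct half-width is 0.160 SD at rho 0.3 and 0.172 SD at rho 0.5.

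Simulation (20,000 data sets per case; 20, 40 and 100 subjects) agrees. The eye-level t-interval covered 93.9% to 94.5% at b = 0.10 and 88.8% to 91.8% at b = 1.00. Keeping the simple mean, but with a subject-clustered standard error and t on G − 1 degrees of freedom, gave 94.3% to 95.3% in every case.

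**(b) Binocular counts**

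Suppose all 100 subjects are bilateral and tested, with both eyes in the same adjustment group. There are then 100 binocular results. Counted in eyes, n = 200. If k subjects reach a threshold, the percent is 2k/200 = k/100, so it does not change; only n doubles. A subject with one eye of each type would contribute one eye to the presbyopia table where others contribute two, so the percent is strictly unchanged only when both eyes share a group.

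Under the synopsis and Section 4, that mixed subject has received a presbyopia adjustment and so cannot be among those who had only non-presbyopic adjustments. The subject belongs to the presbyopia group. What remains is that these sections group by subject and Section 8.1.1 groups by eye.

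**The case against.** Several points on the other side stand, and they limit the finding.

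- **The study is exploratory.** Section 3 defines no primary effectiveness endpoint, and Section 9.1 says no endpoint is hypothesis-driven. This limits the severity. However, Section 9.1 uses that status only to waive a multiplicity adjustment; it does not define the interval or correct a denominator.
- **Silence is not a method.** A reader might infer that the plan treats fellow eyes as independent. It does not say so; it names no method. The narrow interval is what follows if the analyst uses the only unit the plan names.
- **Pairs may be few.** Testing is optional and only subjects with both eyes presbyopia-adjusted and tested supply pairs. At 10% paired, the effect is 3% to 4% in the standard error.
- **Monocular testing is assumed.** Section 7.5 labels the acuity tests monocular or binocular but gives depth of focus neither label. Averaging across eyes makes monocular testing likely, not certain.
- **Some text is not available.** Section 8.2.1, parts of Table 1 and Appendix 1 are not in the text reviewed. A general interval convention there cannot be excluded.
- **The binocular sentence may be shorthand.** It also mentions binocular DCIVA and DCNVA, which Section 7.5 lists only as monocular. Nothing says a binocular value is entered twice, so this is a correction of wording.

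A reader might also infer that a subject with one eye of each type would appear in both adjustment groups, or has no group. The subject-level grouping in the synopsis and Section 4 does not support that. Nor do the documents give the share of such subjects or any difference in their results, so no amount of misattribution can be calculated.

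**Conclusion.** The point holds, at minor severity and on the visible text.

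(a) The depth-of-focus intervals are under-specified. Under the stated assumptions, an eye-level interval is too narrow by a factor between 1.03 to 1.04 (10% of tested subjects paired) and 1.14 to 1.22 (all paired), with coverage from about 94% down to 89%. The upper end needs every tested subject to have both eyes presbyopia-adjusted, so it is a bound for these correlations and not an expectation. A larger correlation would raise the factor by the same formula; the documents give no value.

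(b) Binocular acuity is written in the wrong unit. Read literally, n can reach 200 where there are 100 observations.

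It would be wrong to extend this to the primary exploratory parameters. They are monocular or eye-level proportions with no interval planned, and no test or sample size rests on either part.

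**What to change.** In Section 8.1.1:

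1. Keep the simple mean across eyes. State the confidence level. Compute the interval with subject as the cluster: cluster-robust standard error, independence working correlation, and t with number of subjects minus 1 degrees of freedom. Independence working correlation leaves the plotted mean as planned; an exchangeable structure would down-weight paired eyes when one-eye subjects are present.
2. Report the numbers of eyes and of subjects at each point on the curve.
3. Report binocular acuities as number and percent of subjects.
4. Align the grouping unit with the synopsis and Section 4, so that a subject with one eye of each adjustment type is in the presbyopia group for binocular results. State how many such subjects there are.

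The cost is a few sentences and standard software, with no new data. The downside is wider intervals: about 3% to 22% over the range tabulated. With only 20 subjects, all paired, at rho 0.5, the smaller degrees of freedom bring this to about 27% (1.225 × 2.093/2.023 = 1.27).
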